4.9.5 Other Efficacy Outcomes

Treatment groups will also be compared on the basis of the following additional efficacy outcomes, with tumor response defined by RECIST criteria (version 1.1):

Best Overall Response (BOR)

The BOR is the best response observed from the start of study treatment until the last assessment of tumor response recorded during follow-up or the start of any post treatment cancer therapy (whichever is sooner), taking into account any requirement for confirmation (i.e., at least 4 weeks apart). The number and percentage of subjects in each BOR category (i.e., CR, PR, SD, PD, and unevaluable) will be summarized by treatment group. Subjects with unconfirmed CR or PR assessments will be categorized separately. The table will include a category for subjects who died or discontinued the study due to disease progression prior to the first tumor assessment, as well as ongoing subjects without a tumor assessment prior to the data cut-off date for analysis. Subjects will be classified as having stable disease if assessed as SD (or better) at least 6 weeks after first dose date.

Data listings will display target lesion measurements and non-target lesion response assessments at each timepoint, together with the level of tumor response assigned by the investigator.

Time to Response (TTR)

The TTR is defined as the time interval between the date of randomization and the date of first documented CR or PR. CR or PR requires confirmation at least 4 weeks apart. Once it is confirmed, the first documented CR or PR will be considered as the start of the response. TTR will be descriptively summarized for subjects who responded.

Duration of response (DOR)

The DOR is defined as the time interval between the date of first documented PR or CR and the subsequent first date of disease progression as determined by radiological assessment using RECIST criteria (version 1.1) or death.

Subjects who do not experience disease progression and have not died will be censored on the date of their last tumor assessment. Disease progression that occurs after more than one missed visit (i.e., 12 weeks) will be censored on the date of the last tumor assessment prior to the first

missed visit. For OS, the death date will be used as an event time, no matter how many prior visits were missed.

DOR for subjects who achieve a PR and then a CR will be calculated starting from the date of the PR. Duration of response will be derived as (earliest date of progression or death) – (date of first documented objective response) + 1. Duration of response will be summarized descriptively for each treatment group using Kaplan-Meier methods, as appropriate.

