8.4. EOT/Safety Visit

The following assessments must be completed within approximately 30 days after the time the Investigator decides to discontinue all study drugs for the subject (dinutuximab and/or chemotherapy) or prior to the initiation of subsequent treatment, whichever occurs first. Any ongoing AEs/SAEs at the time of the EOT/safety visit should be followed as outlined in [Section 9.2](#).

- ECOG performance status.
- Status of ongoing AEs and con meds.
- Hematology (including differential).
- Chemistry (BUN, creatinine, glucose, uric acid, bicarbonate, calcium, chloride, phosphorus, potassium, sodium, LDH, albumin, total protein, magnesium, ALP, AST, ALT, total bilirubin).

- Blood samples for post-treatment immunogenicity (**Part 1 and Part 2 Group B only**) **IF** EOT visit occurs within the time frame for the first evaluation (4 weeks [+/- 7 days] of completing dinutuximab) (See [Section 8.5](#)).
- Blood sample for biomarker analysis.
- Blood sample to analyze CTC (**Part 2, selected regions only**).
- Disease assessments (CT or MRI of the chest/abdomen with contrast, with careful attention to the liver and adrenal and other locations as clinically indicated) unless disease progression is previously documented during the study per RECIST.
- Brain MRI (preferred) or brain CT with contrast for subjects with prior evidence of brain metastasis (at baseline) unless disease progression is previously documented during the study per RECIST.
- Recording of planned subsequent anticancer treatment, if any.

Note: All subjects should be followed for overall survival. Subjects enrolled in Part 2 who discontinue treatment prior to the documentation of disease progression should continue to be followed on the disease assessment schedule (every 6 weeks from the date of randomization [+/- 7 days]) until disease progression is documented radiographically per the protocol. At the EOT, further follow-up should be clarified with the subject (for OS, or for disease assessments if applicable) and any such consent for ongoing follow-up must be documented in both the source records and the eCRF. Subject follow-up is critical to prevent or minimize informative censoring for assessment of OS and PFS, the study's primary endpoint and key secondary endpoint, respectively.

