4.9.2 Progression-Free Survival (PFS)

PFS is defined as the time from the date of randomization to the date of first documentation of tumor progression or death from any cause, whichever occurs first. Tumor response assessments will be performed using Response Evaluation Criteria In Solid Tumors (RECIST) version 1.1.

PFS will be evaluated using the stratified log-rank test, as described for OS, with specific conventions for censoring. PFS data will be censored on the date of the last tumor assessment documenting absence of PD for subjects who 1) are given anti-tumor treatment other than the study treatment prior to observing objective tumor progression; 2) are removed from the study prior to documentation of objective tumor progression; 3) are ongoing and do not have objective tumor progression at the time of the analysis. Death or disease progression that occurs after more than one missed visit (i.e., 12 weeks) will be censored on the date of the last tumor assessment prior to the first missed visit. Subjects with no post-baseline tumor assessments will be censored on the date of randomization.

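### Duration of response follows different event and censoring rules from PFS, so the same progression or late death can be an event in one and censored in the other

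*SAP*

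**What the plan says.** **PFS (SAP 4.9.2).** Subjects who "are given anti-tumor treatment other than the study treatment prior to observing objective tumor progression" are censored at their last tumor assessment showing no progression. The missed-visit rule names both kinds of event: "Death or disease progression that occurs after more than one missed visit (i.e., 12 weeks) will be censored on the date" of the last assessment before the first missed visit.

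**DOR (SAP 4.9.5).** DOR runs from first documented response to radiological progression or death. The general rule is "Subjects who do not experience disease progression and have not died will be censored on the date of their last tumor assessment". The missed-visit rule names one kind of event: "Disease progression that occurs after more than one missed visit (i.e., 12 weeks) will be censored on the date of the last tumor assessment" before the first missed visit. The next sentence, "For OS, the death date will be used as an event time", deals with deaths after missed visits for OS only. The derivation begins "Duration of response will be derived as (earliest date of progression or death", subtracts the date of first response and adds one day. New anti-tumor treatment is not mentioned.

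**Related text.** Best overall response (BOR) in SAP 4.9.5 stops at the start of post-treatment cancer therapy. Protocol 10.9.6 counts subjects who receive other anti-tumor therapy before reaching the endpoint as non-responders for ORR and CBR. The same section's DOR paragraph has neither a new-therapy rule nor a missed-visit rule. Under Protocol 8.4, Part 2 subjects who stop treatment without progression stay on the 6-week scan schedule "until disease progression is documented radiographically per the protocol".

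**The concern.** PFS and DOR share their terminal events and differ only in where the clock starts. A reader of the report will expect one subject's progression or death to be handled the same way in both tables. Under the SAP it need not be.

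The situation is foreseeable. Because scanning continues after treatment stops, progression after a switch to another drug will be recorded. It then counts as the end of response in DOR, while PFS has already excluded it.

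At stake is how the DOR summary (SAP Table 14.2.5.1) reads beside the PFS and response tables. SAP 4.9.5 says the treatment groups will be compared on this outcome. In an open-label trial, an unstated rule for switches also leaves a choice to be made after the data are known.

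**Working it through.** No stated figure of the plan is involved. The check sets the rules side by side and then applies them to dated subjects.

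**Rules in the SAP**

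| Situation | PFS (4.9.2) | DOR (4.9.5) |
|---|---|---|
| Other anti-tumor treatment, then progression or death | Censored | Event* |
| Progression after more than one missed visit | Censored | Censored |
| Death after more than one missed visit | Censored | Event |
| Death after one missed visit, no switch | Event | Event |

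*Unless it is a progression that falls under the missed-visit rule.

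The endpoints disagree in the first and third rows. The missed-visit difference concerns deaths only.

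**Conventions.** Randomization is day 1 and scans fall every 42 days (days 43, 85, 127, 169, 211, 253). DOR = event or censoring date − response date + 1, as in the SAP. PFS time = event or censoring date − randomization date + 1. The SAP does not print the +1 for PFS; I use the form that Protocol 10.9.1 gives for OS.

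**Example 1: death after missed scans.** Partial response on day 43, last scan on day 85, scans due on days 127 and 169 missed, death on day 205.
- The gap is 205 − 85 = 120 days, more than 12 weeks (84 days).
- PFS is censored at 85 − 1 + 1 = 85 days.
- DOR is an event at 205 − 43 + 1 = 163 days.

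**Example 2: switch, scans continue.** Partial response on day 43, other treatment started after the day 85 scan, progression on day 253.
- DOR is an event at 253 − 43 + 1 = 211 days.
- If the PFS rule means the last scan before the switch, PFS is censored at 85 days.
- If it is read literally, as the last scan without progression even after the switch, that scan is day 211 and PFS is censored at 211 days, equal to DOR.
- On either reading the progression is an event in DOR and censored in PFS.

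**Example 3: switch, scans stop.** Partial response on day 43, switch after the day 85 scan, death on day 145.
- PFS is censored at 85 days on either reading.
- DOR is an event at 145 − 43 + 1 = 103 days.

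**How many responders.** Protocol 10.11 takes 20% ORR for irinotecan and an odds ratio of 2.0 for its futility target, and there are 184 subjects per arm.
- Group A: 184 × 0.20 = 36.8, about 37.
- Group B: odds 0.20/0.80 = 0.25; 0.25 × 2.0 = 0.5; rate 0.5/1.5 = 0.333; 184 × 0.333 = 61.3, about 61.
- The documents give no rate of switching before progression. An assumed 5% gives 1.8 and 3.1 responders; 30% gives 11.0 and 18.4. The range is about 2–11 in Group A and 3–18 in Group B.

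The documents also give no basis for the number of late deaths after missed scans.

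**With common rules.** In Example 1, DOR would be censored on day 85, at 85 − 43 + 1 = 43 days, beside PFS censored at 85 days. Both would end on the same date with the same status.

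**The case against.** The best defense is that following a response to progression or death whatever treatment comes later is a legitimate choice. It also matches the duration-of-response definition in Protocol Appendix C, which has no new-therapy clause. That stands as a defense of the choice. It does not explain why the plan takes the opposite course for PFS, BOR and the binary response endpoints without saying that DOR is meant to differ. Nor does it explain the missed-visit rule, which censors progression but not death.

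Three stronger readings are tempting, and the documents do not support them.

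- A reader might infer that a DOR longer than PFS is a logical impossibility. It is not: in Examples 1 and 3 an event time is set against a censoring time, and PFS censored at 85 days means at least 85 days. The fault is inconsistent classification.
- A reader might infer that a switch always makes DOR exceed PFS, because PFS stops at the last scan before the switch. SAP 4.9.2 does not say the scan must precede the switch. Read literally, with scans continued, the two times can be equal, as in Example 2.
- A reader might infer that the rule flatters the dinutuximab arm. Counting through a switch lengthens DOR only if the later drug delays progression; otherwise it adds events that censoring would have removed. Nothing in the documents shows which arm would have more switching responders.

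It is also fair to say that the consequence is small. SAP 4.9.5 has DOR summarized descriptively, and it is outside the hierarchy in SAP 4.9.

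**Conclusion.** The inconsistency is real and minor. Applied as written, the SAP treats progression or death after a switch, and death after more than one missed visit, as DOR events while censoring them in PFS. The missed-visit part depends on no disputed reading. For switches, the event-versus-censored mismatch holds on either reading of the PFS rule; only the difference in days depends on the reading.

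The figures of about 2–11 responders in Group A and 3–18 in Group B rest on the futility assumptions for response and on an assumed 5–30% switching rate. They give scale and are not a forecast. The direction of any between-arm effect is unknown. The OS, PFS, ORR and CBR tests and their type I error are unaffected.

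**What to change.** Before database lock:

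1. In SAP 4.9.5, state that DOR uses the same censoring rules as PFS. A responder who starts other anti-tumor treatment before progression is censored at the last no-progression scan preceding that treatment.
2. In the DOR missed-visit sentence, add death alongside progression, as SAP 4.9.2 already does for PFS.
3. In SAP 4.9.2, add to the new-treatment rule that the censoring scan must precede the start of that treatment. Without this, the first change would create a new mismatch.

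If following response through later therapy is intended, the SAP should say so and give the reason.

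The cost is a few lines of SAP text. No new data are needed, because the PFS rule already depends on knowing about other anti-tumor treatment and the SAP plans a listing of post-study cancer therapy. The downside is more censoring in a small group of responders, and the DOR estimate may move in either direction.

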4.9.6 Subgroup Analysis

For exploratory purposes, the analysis of OS will be performed within subgroups of subjects in the ITT Analysis Set defined by the following criteria. The same method used for the analysis of the primary efficacy endpoint (OS) will be applied except that the stratification factor will not be included in the analysis of the prior platinum response subgroups.

- Prior Platinum Response (relapse-free < 3 months vs. \geq 3 months)
- Age Group (< 65 years vs. \geq 65 years)
- Sex (male vs. female)
- Geographic Region (North America/Europe/Asia-Pacific)
- Baseline Tumor Burden (Lowest, Middle, Highest Tertile)
- GD2 expression (positive vs. negative)

In addition, the impact of steroid use on the treatment effect of dinutuximab will be explored.

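### The exploratory OS subgroup analysis tests treatment separately within 14 subgroups but never tests whether the effect differs between them

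*SAP*

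**What the plan says.** SAP 4.9.6 opens: "For exploratory purposes, the analysis of OS will be performed within subgroups of subjects in the ITT Analysis Set". It then says "The same method used for the analysis of the primary efficacy endpoint (OS) will be applied", except that stratification is dropped for the prior platinum response subgroups.

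The factors are prior platinum response (2 levels), age (2), sex (2), region (3), baseline tumor burden (3) and GD2 expression (2).

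The primary method is in SAP 4.9.1: a two-sided stratified log-rank test at 0.05, Kaplan-Meier medians and rates with CIs, and a stratified Cox hazard ratio with 95% CI.

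The places where a comparison between levels might have been planned do not contain one:

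- The Cox covariate model (protocol 10.9.1, SAP 4.9.1) examines the influence of covariates on OS and names no treatment-by-covariate term.
- The sample PHREG code in SAP 7.2.6 has treatment as its only model term.
- SAP 8.1 and 8.3 list OS summaries and Kaplan-Meier plots by subgroup, and prognostic-factor tables, but no interaction table and no forest plot.
- SAP 4.9.6 says the influence of steroid use on the treatment effect will be explored, but gives no method.

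The testing hierarchy in SAP 4.9 covers OS, PFS, ORR and CBR for Group B versus Group A. Subgroups are not part of it.

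**The concern.** A subgroup analysis exists to ask whether the treatment effect is much the same across kinds of patient. A test run inside each level answers another question: is there an effect in this level, given the deaths that happen to fall in it? A significant result in one level and a non-significant one in another is not evidence that the two effects differ, because the second level may simply have too few deaths.

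The protocol (1.14) intends the findings to support registration if warranted. Prior platinum response is the stratification factor and GD2 is the drug's target, so readers will ask about consistency across both. With the output as planned, they would have to compare p-values or judge overlapping intervals by eye.

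**Working it through.** **Inputs.** 306 deaths in Groups A and B, HR 0.725, two-sided alpha 0.05 and about 80% power (SAP 4.2); 1:1 allocation between A and B (184 and 184); factors and levels from SAP 4.9.6. Subgroup shares are not in the documents and are assumed.

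**Number of subgroups.** 2 + 2 + 2 + 3 + 3 + 2 = 14. The tables and figures in SAP 8.1 and 8.3 cover only platinum response, age, region and tumor burden: 2 + 2 + 3 + 3 = 10.

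**Design figure.** Power = Φ(√d × |ln HR| / 2 − 1.96). With d = 306 and |ln 0.725| = 0.3216: Φ(17.49 × 0.1608 − 1.96) = Φ(0.853) = 80.3%. The plan's figure reproduces.

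**Power within a subgroup at HR 0.725.**

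| Share of deaths | Deaths | Power |
|---|---|---|
| 1/2 | 153 | 51% |
| 1/3 | 102 | 37% |
| 1/5 | 61 | 24% |

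**Same effect everywhere (HR 0.725).**

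- With equal splits there are 8 half-size and 6 third-size subgroups. Expected number non-significant: 8 × (1 − 0.512) + 6 × (1 − 0.368) = 3.9 + 3.8 = 7.7 of 14.
- For one factor with two equal halves, the chance that one half is significant and the other is not is 2 × 0.512 × 0.488 = 50%.
- The 14 subgroups overlap, so the chance of at least one non-significant result was simulated: 15,000 trials, 306 deaths each carrying information 1/4, six independently assigned factors. It is 98% with equal splits and 99% with an unequal set (40/60, 55/45, 65/35, 20/60/20, thirds, 80/20). Among trials significant overall it is still 98 to 99%.
- At least one subgroup has an estimated HR above 1 in 28% (equal) to 38% (unequal) of trials.

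**No effect anywhere (HR 1), same simulation.**

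| Set | Any p<0.05 | Any p<0.05 favouring dinutuximab |
|---|---|---|
| 14 subgroups | 38–39% | 19–20% |
| 10 listed subgroups, equal splits | 32% | 16–17% |

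Treating the 14 tests as independent would give 1 − 0.95^14 = 51%, which is too high because the same deaths enter every factor.

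**What one interaction test per factor would do.**

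- Six tests under a uniform effect: 1 − 0.95^6 = 26% chance of at least one p<0.05 (simulated 26 to 27%, at HR 1 and at HR 0.725). Each single test holds 5%.
- Power with two halves of 153 deaths: SE = √(4/153 + 4/153) = 0.229. For a ratio of HRs of 0.725, Φ(0.3216/0.229 − 1.96) = 29%. For a ratio of 0.60 it is 61%, and for 0.50 it is 86%.

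**The case against.** The strongest reply is that nothing depends on these p-values. SAP 4.9.6 calls the analysis exploratory, the hierarchy excludes it, and no rule declares a subgroup positive below 0.05 or without benefit above it. That stands. A reader might infer that subgroup effects are to be judged by within-subgroup significance, but the documents state no such rule.

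Second, the primary method carries hazard ratios with 95% CIs into each subgroup, so much of what a forest plot needs is already planned. That also stands. What is missing is the comparison between levels.

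Third, a reader might infer that a negative trial would probably produce a subgroup that appears to favour dinutuximab. The figures do not support this. The 38% counts results in either direction. The chance of one favouring dinutuximab is about 19 to 20%, and about 17% among trials where the overall test does not favour it.

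Fourth, the 98% reflects low power within subgroups, which an interaction test does not cure. True, and the interaction tests are themselves weak. But an interaction test at least holds its 5% level when the effect is uniform, whereas separate tests in two equal halves disagree half the time.

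**Conclusion.** The point holds as a cheap improvement to an exploratory analysis. As planned, the subgroup output contains no measure of whether the treatment effect differs between levels, and an entirely uniform effect at the design hazard ratio would almost always look uneven on the p-values. Spurious significance under no effect is a moderate risk, not a likely outcome.

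The sizes rest on assumed equal splits and independent factors; the unequal set moves them by only a point or so, apart from the HR-above-1 figure. GD2 could depart furthest from these splits, because the only sample the protocol (8.2) ties by name to gangliosides is an optional, archival, fresh-frozen one.

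The primary OS test, its type I error and the secondary hierarchy are unaffected.

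**What to change.** In SAP 4.9.6, replace the repeated primary test with one model per factor: a Cox model in Groups A and B with treatment, factor and treatment-by-factor interaction, stratified by prior platinum response except when that is the factor examined. Report one interaction p-value per factor beside the hazard ratio and 95% CI for each level, in a forest plot. Drop the within-subgroup log-rank p-values.

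State that the interaction tests are descriptive, that their power is low, that six of them leave roughly a one-in-four chance of a p<0.05 under a uniform effect, and that they are to be read with the CIs.

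At the same time, add sex and GD2 to the lists in SAP 8.1 and 8.3, and say how the five regions in SAP 7.2.3 map to the three in 4.9.6.

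The cost is SAP wording, one model per factor and one figure. No new data, sample size change or endpoint change is needed.

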4.10 Safety Analysis

4.10.1 Adverse Events – Part 1

Toxicities reported during Part 1 (intrasubject dose escalation) will be listed for individual subjects by dinutuximab dose at time of onset. Pain severity scores will also be listed by dinutuximab dose, cycle, and time since start of infusion.

4.10.2 Adverse Events – Part 2

AEs will be coded using MedDRA Version 20.0 or higher. Treatment-emergent AEs (TEAEs) will be grouped and tabulated by the MedDRA System Organ Class (SOC) and Preferred Term (PT). An AE that starts or increases in severity after the first dose of study medication and up

until 30 days after the last dose will be considered a TEAE. Severity of the AEs will be graded according to the NCI CTCAE Version 4.03.

All safety summaries will be generated for the Safety Analysis Set.

A safety overview table will present the number (%) of subjects in each treatment group with events in the following categories:

- Any TEAEs
- Treatment-Related TEAEs
- Grade ≥ 3 TEAEs
- Grade ≥ 3 Treatment-Related TEAEs
- Treatment-Emergent Serious Adverse Events (SAEs)
- Treatment-Related SAEs
- Grade ≥ 3 SAEs
- Grade ≥ 3 Treatment-Related SAEs
- TEAEs leading to Discontinuation of Study Treatment
- TEAEs leading to Reduction in Dose of Study Treatment
- Fatal TEAEs
- Fatal Treatment-Related TEAEs

For these events, the difference between incidence rates for Group B (dinutuximab + irinotecan) minus Group A (irinotecan) will be presented, together with its 2-sided 95% confidence interval calculated using the Wilson score method. A lower bound $>$ zero may indicate excess risk in the dinutuximab group. The Wilson score method will be used to calculate 95% confidence intervals to ensure actual coverage closest to the nominal level.

The number and percentage of subjects experiencing TEAEs will also be summarized by SOC and PT. The following tables will be generated:

- Overall TEAEs
- Dinutuximab-Related TEAEs
- Irinotecan/Topotecan-Related TEAEs
- Grade ≥ 3 TEAEs,
- Dinutuximab-Related Grade ≥ 3 TEAEs
- Irinotecan/Topotecan-Related Grade ≥ 3 TEAEs
- TEAEs leading to discontinuation of Dinutuximab

- TEAEs leading to discontinuation of Irinotecan/Topotecan
- TEAEs leading to dose reduction of Dinutuximab
- TEAEs leading to dose reduction of Irinotecan/Topotecan
- Treatment-emergent SAEs
- Treatment-emergent SAEs related to Dinutuximab
- Treatment-emergent SAEs related to Irinotecan/Topotecan
- TEAEs with an outcome of death
- TEAEs by Maximum Grade
- TEAEs of special interest

Adverse events of special interest are defined as:

- Severe non-hematologic toxicities including allergic reactions (anaphylaxis)
- Severe neuropathic pain unresponsive to treatment
- Prolonged motor weakness (>2 weeks in duration)
- Acute Grade 4 vascular leak syndrome
- Grade 3 visual toxicity

By-subject data listings of AEs will provide the AE verbatim term, SOC, PT, onset date/day relative to start of study treatment, severity, outcome, and relationship to study treatment. Separate listings will be generated for all AEs (regardless of treatment emergence), Grade ≥ 3 AEs, all treatment-related AEs, all SAEs, AEs that lead to discontinuation of any study treatment, AEs with a fatal outcome, and all deaths. The listing of deaths will include the date and cause of death, number of days from randomization, and number of days from last dose of study treatment.

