9.2. Documentation of Adverse Events

An AE or SAE occurring during the study must be documented in the subject's source documents and on the appropriate eCRF page. Information relating to the AE such as onset and cessation date and times, severity (see definitions in NCI-CTCAE v4.03), relationship to study drug, and outcome is also to be documented in the eCRF (see [Appendix B](#) for definitions). Where possible, AEs should be recorded using standard medical terminology. If several signs or symptoms are clearly related to a medically defined diagnosis or syndrome, the diagnosis or syndrome should be recorded on the eCRF page, not the individual signs and symptoms.

All AEs should be followed until either resolution (or return to normal or baseline values), until they are judged by the Investigator to no longer be clinically significant, or for at least 30 days if the AE extends beyond the final visit. All SAEs that occur during the study will be followed until resolution, death, or the subject is lost to follow-up even if they are ongoing more than 30 days after completion of the final visit. Supplemental measurements and/or evaluations may be necessary to investigate fully the nature and/or causality of an AE or SAE. This may include additional laboratory tests, diagnostic procedures, or consultation with other healthcare professionals. The eCRF pages should be updated with any new or additional information as appropriate.

Fatal events that occur after 30 days from the last dose of study drug will be entered into the EDC as events for the primary endpoint analysis and do not need to be reported to UT GDS unless the Investigator believes the event to be related to study drug.

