10.10. Safety Analyses

Safety data, including AEs, SAEs, vital signs, clinical laboratory evaluations, and treatment discontinuation due to toxicity, will be summarized descriptively. Univariate descriptive statistics, including mean, standard deviation, median, and range will be presented for continuous variables. Frequency tables will be used to present categorical data. All summaries will be prepared for the Safety Analysis Set. For each safety parameter, the last assessment made before the first dose of study treatment will be used as baseline for all analyses of that safety parameter.

10.10.1.Toxicities - Part 1

Toxicities reported during Part 1 (intrasubject dose escalation) will be listed for individual subjects and summarized by dinutuximab dose at time of onset. Pain severity scores and detailed pain medication log will also be listed by dinutuximab dose, cycle, and time since start of infusion and will be submitted with the Clinical Study Report.

10.10.2.Adverse Events

AEs will be coded using the current version of the Medical Dictionary for Regulatory Terms (MedDRA). TEAEs will be grouped and tabulated by the MedDRA System Organ Class (SOC) and Preferred Term (PT). An AE that starts or increases in severity after the first dose of study medication will be considered a TEAE. Severity of the AEs will be graded according to the NCI CTCAE Version 4.03. TEAEs will be summarized by treatment group, severity, and relationship to study drug. The number and percentage of subjects experiencing at least one TEAE will be displayed by SOC and PT in each treatment group for the Safety Analysis Set.

Additional summary tables will be generated for grade 3 or higher TEAEs, TEAEs considered related to study medication (possibly + probably + related), TEAEs by severity and relationship, deaths, SAEs, and TEAEs leading to treatment discontinuation.

A by-subject AE data listing will present each AE verbatim term, SOC, PT, onset date/day relative to start of study treatment, severity, outcome, and relationship to study treatment. Separate listings will be generated for deaths, SAEs, and AEs leading to treatment

discontinuation. The listing of deaths will include the date and cause of death, number of days from randomization, and number of days from last dose of study treatment.

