3.1 Changes in the conduct of the study or planned analyses

Not applicable.

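### The SAP's 30-day TEAE window leaves a drug-related fatal AE with onset after day 30 out of every fatal-event count, although the protocol has no such cut-off and keeps these deaths reportable

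*SAP*

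**What the plan says.** **Protocol.** Section 10.10.2 defines treatment emergence by its start only: "An AE that starts or increases in severity after the first dose of study medication will be considered a TEAE". It also plans a summary table of deaths. Section 9.2 treats late deaths separately. It has deaths more than 30 days after the last dose recorded in the EDC for the OS analysis, and says of them that they "do not need to be reported to UT GDS unless the Investigator believes the event to be related to study drug". A late death judged related thus remains a reportable safety event.

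**SAP.** Section 4.10.2 uses the same opening, "An AE that starts or increases in severity after the first dose of study medication and up", and then closes the window: "until 30 days after the last dose will be considered a TEAE". The data-handling rules in 7.2.5 deal with missing and partial dates and add no exception for relatedness. The fatal counts are all restricted to TEAEs: the fatal-TEAE row of the overview, the row "Fatal Treatment-Related TEAEs", the SOC/PT table "TEAEs with an outcome of death", and Table 14.3.1.12. The table list in 8.1 has no summary of all deaths. Section 1 undertakes to identify substantial differences from the protocol, but 3.1, on changes to planned analyses, reads "Not applicable".

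**The concern.** The protocol singles out one kind of event after day 30 as still mattering for drug safety: a death that the investigator attributes to study drug. The SAP's counts omit such a death when its AE began after day 30, and the change is undeclared.

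The overview rows are not merely descriptive. For each of them SAP 4.10.2 presents the Group B minus Group A difference with a two-sided 95% interval, and a lower bound above zero is read as possible excess risk with dinutuximab. Related fatal counts may be small, so a single event could decide that reading.

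**Working it through.** **Step 1: which events drop out.** The SAP's test is the date the AE starts or worsens. Protocol 9.2 is keyed to the date of the fatal event. The two rules therefore cover different sets. Days are counted from the last dose, and the AE is judged related and fatal:

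| AE onset | Death | Reportable under Protocol 9.2 | TEAE under Protocol 10.10.2 | TEAE under SAP 4.10.2 |
|---|---|---|---|---|
| day 30 | day 45 | yes | yes | yes |
| day 31 | day 45 | yes | yes | no |

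Only the second row is affected.

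**Step 2: where it is lost.** It is certainly missing from the four fatal counts named above, because each is limited to TEAEs. For related SAEs the SAP is unclear. The overview rows for treatment-related SAEs and Grade 3 or higher treatment-related SAEs, and the titles of Tables 14.3.1.9.1 to 14.3.1.9.3, do not mention treatment emergence. The SOC/PT list in 4.10.2 does.

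**Step 3: could one event matter?** The plan gives no figure to reproduce and no expected number of late related deaths, so this is illustration only. Inputs: 184 subjects per group (SAP 4.2, taking all as treated); the Wilson score method (SAP 4.10.2), taken as Newcombe's interval for a difference; assumed event counts.

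For x events in n, with p = x/n and z = 1.96, the Wilson limits l and u are

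[p + z²/(2n) ± z·√(p(1−p)/n + z²/(4n²))] / (1 + z²/n).

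The lower limit for B minus A is

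(pB − pA) − √[(pB − lB)² + (uA − pA)²].

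- 5 vs 0: pB = 5/184 = 0.02717, lB = 0.01166, uA = 0.02045. Lower limit = 0.02717 − √(0.01551² + 0.02045²) = 0.02717 − 0.02567 = 0.0015.
- 4 vs 0: pB = 4/184 = 0.02174, lB = 0.00849, uA = 0.02045. Lower limit = 0.02174 − √(0.01325² + 0.02045²) = 0.02174 − 0.02437 = −0.0026.

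| Assumed related fatal events, B vs A | Difference | Lower 95% limit | Flagged |
|---|---|---|---|
| 5 vs 0 | 2.72% | 0.15% | yes |
| 4 vs 0 | 2.17% | −0.26% | no |
| 7 vs 1 | 3.26% | 0.11% | yes |
| 6 vs 1 | 2.72% | −0.31% | no |
| 9 vs 2 | 3.80% | 0.19% | yes |
| 8 vs 2 | 3.26% | −0.25% | no |

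In each pair, excluding one Group B event removes the flag. These pairs sit at the threshold by construction; away from it, one event changes the rate but not the flag.

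**The case against.** **A 30-day window fits the rest of the safety collection.** Concomitant medications stop at about 30 days (Protocol 6.11), Protocol 9.2 itself uses 30 days, and AE assessment is scheduled only up to the end-of-treatment visit. Protocol 10 leaves data-handling conventions to the SAP, and the SAP states that it supersedes the protocol. For non-fatal events this largely stands. The alignment is imperfect, because Protocol 8.4 times the end-of-treatment visit from the decision to stop. If that decision is made when the next 21-day cycle falls due, the visit can come about 21 + 30 = 51 days after the last dose. For fatal events the objection does not stand, because Protocol 9.2 expressly carries related deaths past day 30.

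**The deaths are not hidden.** SAP 4.10.2 lists all AEs regardless of emergence, related AEs, SAEs, fatal AEs and all deaths with days since last dose. Deaths are OS events, and the DMC reviews their number and causes by group. This is right, and it limits the point. A reader might infer that every related death after day 30 disappears, or that it survives only in the all-AE listing; neither is so. But a listing gives no group rate, and OS does not separate related deaths.

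**An open-ended window could bias the comparison.** In Part 2 only Group B returns for sampling at 4, 8, 12 and 16 weeks after the last dinutuximab dose (Protocol 8.5). Counting all late related AEs would give that arm more chances to report them in an open-label trial. This stands, and is why the remedy is confined to fatal events, which are sought monthly in every arm.

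**The loss need not fall on Group B.** A reader might infer that it does because the antibody persists. The cited mean terminal half-life is 181 hours (Protocol 1.9), so 30 days is 720/181 = 4.0 half-lives, leaving about 6%. Irinotecan is given in both arms, and the documents give no late-toxicity rate by arm.

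**Conclusion.** The point holds for one defined set: fatal AEs judged related to study drug whose onset is more than 30 days after the last dose. They are reportable under Protocol 9.2 and would be TEAEs under Protocol 10.10.2, but are outside every fatal-event count in the SAP, and SAP 3.1 does not say so. Whether they are also outside the related-SAE counts cannot be settled from the text; that ambiguity needs resolving.

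The direction is certain, since a shorter window can only lower the counts. The size is not known and may be zero. A reader might put a percentage on it: one late event among six is 17%, two among four is 50%. Such figures only restate the assumed counts. What can be said is that, near the threshold, one omitted event is enough to reverse the SAP's own excess-risk reading, given 184 treated subjects per group and the Newcombe form of the interval. The primary OS analysis is untouched. This is a modest but worthwhile correction to the safety summaries.

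**What to change.** 1. In SAP 4.10.2 and Table 14.3.1.12, count a fatal AE judged related to any study drug whatever its onset after first dose. Keep the 30-day window for non-fatal events.
2. Add the summary table of all deaths that Protocol 10.10.2 promises, by group, relatedness and time since last dose (30 days or less, more than 30 days).
3. State whether the overview rows for treatment-related SAEs and Tables 14.3.1.9.1 to 14.3.1.9.3 are limited to treatment-emergent events, and label them accordingly.
4. Record the 30-day cut-off in SAP 3.1 as a difference from Protocol 10.10.2.

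The cost is a few sentences, one derivation rule and one table. It also requires a check that each late related death reported to drug safety has an AE record with onset date and causality in the EDC, because Protocol 9.2 enters late deaths there as endpoint events. The downside is that late inclusion rests on an open-label causality judgement. The deaths table, which shows all deaths whatever their attribution, lets a reader see how much depends on it.
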